6.2.2. Tipping Point

The following seeds will be used for the tipping point analyses:

Endpoint	Initial Seed
Participants alive and free of respiratory failure at Day 28	1227
Participants alive and free of respiratory failure at Day 60	28903
All-cause mortality at Day 28	29843
All-cause mortality at Day 60	87712

The seeds were generated using the following code:

```
DATA seeds;
DO i=1 to 4;
```

```
seed=int(100000*ranuni(21409402));  
OUTPUT;  
END;  
RUN;
```

6.2.3. Time to Event Model Checking

For the Cox proportional hazards model, the proportional hazards assumption will be assessed prior to model fitting using the following methods:

- Plot of $\log(-\log(\text{survival}))$ versus $\log(\text{time})$ by treatment group: A non-parallel pattern is an indication of violation of the proportional hazard assumption.
- Plot of weighted Schoenfeld residuals versus time: A non-zero slope is an indication of a violation of the proportional hazard assumption.
- Evaluation of time-dependency of treatment effect by adding an interaction term of treatment and time in the Cox model. If the interaction term is significant ($p < 0.05$), it is considered that the proportional hazards assumption is violated.

If one or more of the procedures above demonstrates clear violation of the proportional hazards assumption, it will be considered the proportional hazards assumption does not hold.

6.2.4. Count Data Model Checking

Distributional assumptions underlying the model used for analysis will be checked. If there are any departures from the distributional assumptions, alternative models may be explored as sensitivity analyses.

6.3. Appendix 3: Selected Considerations for Data Analyses and Data Handling

6.3.1. Assessment Windows

All data, except efficacy data, laboratory assessments, and vital signs assessments will be reported according to the nominal time of clinic visits and assessments as specified in the protocol. Laboratory and vital signs assessments will be analyzed based on the visit information recorded in the eCRF. Data for unscheduled visits will be assigned to a scheduled visit if the visit date falls within the corresponding visit window as specified below. For statistical analysis it is important to keep the intermediate data, so for efficacy data, visit slotting will be conducted in addition to the actual timepoint. Lab, vital signs, and efficacy data will be slotted according to the windows specified below. Where data is collected daily, this will be analyzed based on the data recorded in the eCRF.

In case of multiple assessments slotting to the same visit, nominal visit will take precedence. If two assessments slot to the same visit and does not include the nominal visit, then the one closest to the nominal visit will take precedence with the last assessment taking precedence if they are equidistant from the nominal visit.

Analysis Set / Domain	Parameter (if applicable)	Target	Analysis Window		Analysis Timepoint
			Beginning Timepoint	Ending Timepoint	
LAB	All	Day 4	Day 3	Day 5	4
		Day 7	Day 6	Day 8	7
		Day 14	Day 13	Day 15	14
		Day 28	Day 27	Day 29	28
Vital Signs	Blood pressure, pulse, respiratory rate and temperature	Day 4	Day 3	Day 5	4
		Day 7	Day 6	Day 8	7
		Day 14	Day 13	Day 15	14
		Day 28	Day 27	Day 29	28
Efficacy	Ventilation Status, Clinical Status, signs and symptoms of COVID-19	Day 4	Day 3	Day 5	4
		Day 7	Day 6	Day 8	7
		Day 14	Day 12	Day 16	14
		Day 28	Day 26	Day 30	28
		Day 42	Day 40	Day 44	42
		Day 60	Day 53	Day 67	60

6.3.2. Derived and Transformed Efficacy Data

6.3.2.1. Ventilation Status

Ventilation status as shown below, will be derived for Days 1-60 based on the log-based collection (start and end dates/time).

Code	Decode
1	None
2	Low flow oxygen therapy
3	High-flow oxygen therapy (>= 15 L/min)
4	Non-invasive mechanical ventilation
5	Invasive mechanical ventilation
6	Death
99	Other

Ventilation status at baseline is defined as the ventilation status at the time of dosing, if no ventilation is recorded then the last ventilation use will be assigned to baseline. If multiple ventilation types are being used at the start of baseline the worst case is assumed.

For post-baseline the worst-case ventilation on a day will be used, Other will only be considered worst-case if no other ventilation is recorded.

Ventilation statuses with missing end-dates will be assumed ongoing.

Ventilation status will only be missing after last contact for subjects who have withdrawn from the trial, such that participants with no open ventilation logs will be assumed to have Ventilation=None.

Other will not be included in figures

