IV dosing with otilimab or placebo		X						Approximately 1-hour IV infusion. Record start and end times of the infusion. Randomization and Dosing should be as close as possible on the same day.

1. Assessment to be conducted on Days 4 and 7 (if not discharged).
2. Assessment to be conducted every day from Day 1 until Discharge (or until Day 28 if the participant remains hospitalized).
3. Up to 48 h before randomization. If Screening and Randomization are within 24h, there is no need to repeat Day 1 pre-dose assessments (except Ordinal Scale and pre-infusion vital signs).
4. Consent may be collected before the 48h screening window if the investigator considers that the participant is likely to become eligible, and wants to ensure that consent is given by the participant (rather than an LAR).
5. If the participant is discharged before Day 13, the Day 14 and Day 28 visits will be replaced with a phone call (± 2 days). If the participant is discharged on Day 13, the Day 14 visit is not required, and the Day 28 visit will be a phone call (± 2 days). When visits are replaced with a phone call, complete the same assessments as the Day 42 or 60 phone call.
6. If the participant is discharged between Day 15 and Day 27, the Day 28 visit will be replaced with a phone call (± 2 days). When visits are replaced with a phone call, complete the same assessments as the Day 42 or Day 60 phone call.
7. Follow-up phone calls at Day 42 (± 2 days) and Day 60 (± 2 days). If the participant has not been discharged, these will be visits.
8. See Section 6.7 for information on Early Withdrawal.
9. At Screening, record COVID-19 current vaccination status, and any other prior medications within 14 days before Screening.
10. If a cytokine release syndrome (CRS) related to drug is suspected (see Section 7.4.7.1), the following samples should be taken as soon as possible after suspected CRS onset and again 24 h later: Hematology, CRP, D-dimer, ferritin, PD sample (cytokines).
11. Sample can be collected anytime from Screening up to start of infusion.
12. Days 2, 4 and 7 only.
13. Immediately after infusion.
14. Days 2 and 7 only.
15. If central laboratory kits for PK/PD sampling are not available at a site (for operational reasons), participants can be randomised and dosed, and the PK or PD samples not collected (refer to Section 7.5 and Section 7.7).

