4.3.1. Endpoint Definition

4.3.1.1. All-cause Mortality at Day 28 and 60

Participants will meet the endpoint if they have died due to any cause prior to Day 28 and 60. All-cause mortality will be based on the clinical status as defined in Section 6.3.2.

4.3.1.2. Time to All-cause Mortality up to Day 60

Defined as the time (days) from dosing to death, due to any cause, up to (and including) Day 60.

4.3.1.3. Participants Alive and Free of Respiratory Failure at Day 7, 14, 42, and 60

Defined as per primary endpoint, see Section 4.2.1.

4.3.1.4. Time to Recovery from Respiratory Failure up to Day 28

Defined as the time (days) from dosing to last recovery from respiratory failure up to (and including) Day 28. Participants are in respiratory failure if they are in category 5 or above from the GlaxoSmithKline (GSK) modified ordinal scale adapted from World Health Organization (WHO, 2020) scale 2020 (Table 2).

Note: if a participant has recovered from respiratory failure but then progresses back into respiratory failure on or prior to the end of follow up (Day 28) the participant has not had their last recovery from respiratory failure.

This endpoint will use a composite approach for death such that if the intercurrent event of death occurs (on or prior to Day 28), then time will be censored at end of follow up (Day 28).

4.3.1.5. Participants Alive and Independent of Supplementary Oxygen at Day 7, 14, 28, 42, and 60

Participants are independent of supplementary oxygen if they are in category 1, 2 or 3 from the GlaxoSmithKline (GSK) modified ordinal scale adapted from World Health Organization (WHO, 2020) scale 2020 (See Table 2- Ordinal Scale). Missing data prior to study withdrawal will be derived using ventilation data as described in Section 6.3.2

Participants will meet the endpoints if they are alive and independent of supplementary oxygen at Day 7, 14, 28, 42, and 60 respectively. As participants may be discharged from investigator site, analysis windows will be used to define the endpoint as described in Section 6.3.1.

4.3.1.6. Time to Last Dependence on Supplementary Oxygen up to Day 28

Defined as the time (days) from dosing to last dependence on supplementary oxygen up to (and including) Day 28. Participants are dependent on supplementary oxygen if they are in category 4 or above from the GlaxoSmithKline (GSK) modified ordinal scale adapted from World Health Organization (WHO, 2020) scale 2020 (Table 2).

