6.3.2.2. Clinical Status Ordinal Scale

Additional derivation of clinical status will be performed. If subject dies then their clinical status will be recorded as 8-Death from date of death to Day 60 inclusive, this will override any collected clinical status.

Otherwise if clinical status is missing and the assessment day is prior to last contact with participant, then the following rules will apply:

Category	Rule
8 - DEATH	Date of death <= date of assessment
7 - HOSPITALIZED, MECHANICAL VENTILATION+ADDITIONAL ORGAN SUPPORT	Ventilation = "INVASIVE MECHANICAL VENTILATION" and additional support includes: "EXTRACORPOREAL MEMBRANE OXYGENATION" "RENAL REPLACEMENT THERAPY (RRT)/DIALYSIS" "INOTROPES/VASOPRESSORS"
6 - HOSPITALIZED, INTUBATION AND MECHANICAL VENTILATION	Ventilation = "INVASIVE MECHANICAL VENTILATION" and does not meet the classification for additional organ support

Category	Rule
5 - HOSPITALIZED, HIGH-FLOW OXYGEN(\geq 15L/MIN), CPAP, BIPAP, NIV	Ventilation is: "NON-INVASIVE MECHANICAL VENTILATION" or "HIGH-FLOW OXYGEN THERAPY (\geq 15 L/MIN)"
4 - HOSPITALIZED, LOW-FLOW OXYGEN BY MASK OR NASAL PRONGS	Ventilation = "LOW-FLOW OXYGEN THERAPY" and date of discharge to non-hospitalized residence is missing or greater than date of assessment
3 - HOSPITALIZED, NO OXYGEN THERAPY	Date of assessment < date of discharge to non-hospitalized residence and Date of assessment > date of last oxygen usage
2 - NON-HOSPITALIZED, LIMITATION OF ACTIVITY	Date of assessment > date of discharge to non-hospitalized residence and participant has not been re-hospitalized and date of assessment > date of last oxygen usage and does not meet the classification for group 1.
1 - NON-HOSPITALIZED, NO LIMITATION OF ACTIVITY	Date of assessment > date of discharge to non-hospitalized residence and participant has not been re-hospitalized and date of assessment > date of last oxygen usage and last and subsequent recorded assessment is "1 - NON-HOSPITALIZED, NO LIMITATION OF ACTIVITY".

All non-Death derived values will be flagged in the dataset.

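### Part 2 SAP: an open high-flow, NIV or IMV log is carried past discharge, so a participant at home can be derived as hospitalized and in respiratory failure on days with no collected status

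*SAP*

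**What the plan says.** All SAP references are to the Part 2 SAP.

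- **Ventilation record (6.3.2.1).** Status is derived for Days 1 to 60 from start and end dates in a log. "Ventilation statuses with missing end-dates will be assumed ongoing". Where records overlap, "For post-baseline the worst-case ventilation on a day will be used".
- **Trigger for deriving clinical status (6.3.2.2).** Death overrides everything. "Otherwise if clinical status is missing and the assessment day is prior to last contact with participant, then the following rules will apply".
- **Category rules (6.3.2.2).** Category 4 needs low-flow oxygen and that the "date of discharge to non-hospitalized residence is missing or greater than date of assessment". Category 5 needs only a high-flow or non-invasive ventilation record. Categories 6 and 7 need only invasive ventilation, without or with organ support. All three carry a hospitalized label, and none refers to discharge. Categories 1 and 2 need a date after discharge home and after last oxygen use.
- **When status is collected (Protocol 1.4, footnotes 2 and 5 to 7).** For the ordinal scale: "Assessment to be conducted every day from Day 1 until Discharge". After discharge it is collected at the calls only, each within ±2 days.
- **Use of the status.** Sections 4.2.1 (primary), 4.3.1.1 and 4.3.1.5 refer to Section 6.3.2. Section 4.3.1.4 (time to recovery) counts category 5 or above as respiratory failure, takes the last recovery, and says that "if a participant has recovered from respiratory failure but then progresses back into respiratory failure" by Day 28, the last recovery has not happened. It does not refer to Section 6.3.2.

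**The concern.** Between discharge and the next call there is no collected status, so the derivation supplies it for each of those days that precedes last contact. If the site did not end-date a high-flow, NIV or IMV record, the rules return category 5 or worse for someone who has gone home. Categories 1 and 2 cannot apply, because oxygen use never ends in the record. No section closes a log at discharge.

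Time to recovery is test 4 in Section 2.1, and test 5 depends on it. Because it uses the last recovery, a run of derived category 5 days after discharge delays the event or removes it. The primary endpoint also draws on the derivation when Day 28 status is missing. The exploratory time to a 2-category improvement and days per category (4.4.1.11, 4.4.1.12) rest on the same clinical status.

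**Working it through.** **1. The rules applied to one participant.** Discharged home on Day 10, last contact Day 60, status not collected on Day 20 or Day 28.

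| Ventilation log | As written | Category 4 check copied to 5-7, nothing else changed |
|---|---|---|
| High-flow, no end date | 5 | no category |
| NIV, no end date | 5 | no category |
| IMV, no end date | 6 (7 with organ support) | no category |
| High-flow with no end date, plus low-flow ended Day 10 | 5 (worst record) | no category |
| Low-flow, no end date | no category | no category |
| High-flow, ended Day 9 | 1 or 2 | 1 or 2 |

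If a status is collected on Day 28, it stands in every row. A participant with no category stays missing, which for the binary endpoints means imputation under missing at random (4.1.5, 6.2.1).

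**2. Time to recovery, if it uses the derived status.** Take a participant who recovered on Day 9, went home on Day 12, was recorded well at calls on Days 14 and 28, and has a high-flow log with no end date. Inpatient status to Day 12 was collected and stands. Day 13 and Days 15 to 27 are derived as category 5, so last recovery moves from Day 9 to Day 28. If the last call falls on Day 29, Day 28 is itself derived as category 5 and there is no event, unless visit slotting (6.3.1) assigns the Day 29 status to Day 28. The SAP does not settle this. The primary endpoint, with its Day 26-30 window, would still count a responder.

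**3. Primary endpoint: the plan's figure first.** Inputs from SAP Section 5: N = 346, placebo 45%, difference 15 points (so otilimab 60%), one-sided 2.5%. Allocation is 1:1 (Protocol 8.2), so n = 173 per arm. With p̄ the mean of the two rates,

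power = Φ{[d√n − 1.96·√(2p̄(1−p̄))] / √(p₁(1−p₁) + p₂(1−p₂))}

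For p₁ = 0.45, p₂ = 0.60: [0.15 × 13.153 − 1.96 × 0.7062] / 0.6982 = 0.843, and Φ(0.843) = 80.05%. The stated 80% is reproduced.

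**4. Sensitivity.** The documents give no count of open logs, so the fraction m of true Day 28 responders turned into non-responders, equal in both arms, is an assumption. Each rate becomes p(1 − m).

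| m | Rates | Difference | Power |
|---|---|---|---|
| 0 | 45.00% vs 60.00% | 15.00 points | 80.0% |
| 1% | 44.55% vs 59.40% | 14.85 points | 79.2% |
| 2% | 44.10% vs 58.80% | 14.70 points | 78.4% |
| 5% | 42.75% vs 57.00% | 14.25 points | 75.7% |

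Planned responders number 173 × (0.45 + 0.60) = 181.65, so 1% to 5% is about 2 to 9 people.

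**The case against.** The trigger is narrow. Status must be missing, the day must precede last contact, and a high-flow, NIV or IMV log must be open. A reader might infer that participants at home are generally derived as hospitalized; they are not, since a log ended before discharge gives category 1 or 2. This stands and limits the scope.

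For Day 28, the ±2-day call matches the analysis window, and Protocol Section 7 presses sites to complete that call on the day. Failure needs a missed window, a later contact and an uncorrected log together. This stands too.

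Open logs can be caught. Ventilation status is scheduled daily to discharge and again at calls (Protocol 1.4), oxygen at home is recorded at calls (7.2.4), the sponsor checks data quality (9.1.7), and derived values are flagged (6.3.2.2). That should reduce the number, but none of it says what happens to a log that remains open; the SAP's rule does, and gives the wrong answer.

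The effect on test 4 is not certain. Section 4.3.1.4 does not cite 6.3.2, and Section 6.3.1 analyses daily data as recorded while slotting visits in addition. So the claim must be conditional. Test 4 also counts only if all prior tests succeed.

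Finally, classing a participant truly on NIV at home as in respiratory failure may be a defensible conservative choice. The ordinal-scale table is redacted, so this cannot be called an error. The defect concerns stale logs.

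**Conclusion.** As written, the two sections together give a wrong status for a participant discharged home with an uncorrected open high-flow, NIV or IMV log, on each day before last contact without a collected status. This is a stated rule with a wrong result, not a missing detail.

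The main exposure is time to recovery, on the condition that it uses the derived daily status. One stale log can then move a recovery by weeks (Day 9 to Day 28 in the example) or remove it. How many participants this touches cannot be said from the documents.

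The primary endpoint is exposed only in the narrow case above. At an assumed 1% to 5% of responders misclassified equally in both arms, power falls to between 79.2% and 75.7%. A reader might infer that the primary result is in serious doubt, or that the error favours one arm. The documents support neither: they give no frequency, and the logs are completed under blinding, so no difference between arms is shown.

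**What to change.** 1. **6.3.2.1:** close a ventilation or oxygen log with no end date at the date of discharge to a non-hospitalized residence, unless home use is recorded at a later contact or the participant is re-hospitalized. Later days then fall after last oxygen use and come under categories 1 and 2.
2. **6.3.2.2:** state which category applies to participants with recorded oxygen or ventilation at home. At present, low-flow oxygen at home fits no category.
3. **4.3.1.4:** state that time to recovery uses this derived daily status.

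Two simpler repairs should be avoided. Copying the category 4 discharge check to categories 5 to 7 alone leaves the participant with no category, including one truly on NIV at home, and sends that person to imputation. Letting the next call's status overwrite earlier derived days, without an exception for re-hospitalization, could erase a real relapse.

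The cost is a few sentences of SAP text and a small programming change. It should be made before Part 2 is unblinded, because correcting individual recovery dates afterwards would look post hoc.

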6.8. Lost to Follow Up

A participant will be considered lost to follow-up if he or she is unable to be contacted by the study site after discharge from hospital. Every effort must be made to reduce missing data.

- The site must attempt to contact the participant as soon as possible and counsel the participant on the importance of maintaining the assigned study schedule and ascertain whether or not the participant wishes to and/or should continue in the study.
- Before a participant is deemed lost to follow up, the investigator or designee must make every effort to regain contact with the participant (where possible, 3 telephone calls and, if necessary, a certified letter to the participant's last known mailing address or local equivalent methods). These contact attempts should be documented in the participant's medical record.
- Should the participant continue to be unreachable, he/she will be considered to have withdrawn from the study.

Discontinuation of specific sites or of the study as a whole is described in Section 9.1.9.

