4.4.1.4. Alive and Not Invasively Mechanically Ventilated

Participants will meet the endpoint if they are alive and not requiring invasive mechanical ventilation at Day 7, 14, 28, 42 and 60. This will be evaluated only for participants supported using invasive mechanical ventilation at baseline. This will be derived from the worst-case ventilation record as detailed in Section 6.3.2.1.

4.4.1.5. Time to Definitive Extubation up to Day 28

For participants supported using invasive mechanical ventilation at baseline this is defined as the time from dosing (days) to final extubation from invasive mechanical ventilation up to (and including) Day 28. This will be derived from the worst-case ventilation record as detailed in Section 6.3.2.1.

This endpoint will use a composite approach for death such that if the event intercurrent event of death (on or prior to Day 28) occurs, then time will be censored at the end of follow-up (Day 28), including those that were extubated prior to death.

4.4.1.6. Oxygen-free Days up to Day 28

A participant is considered oxygen free on a day if they are not using oxygen (Ventilation=None) as derived from the worst case ventilation record on a day as detailed in Section 6.3.2.1.

Intermittent data is expected after discharge from investigator site, therefore if participants have discontinued oxygen and have been discharged to a non-hospitalized residence, they will be considered to be oxygen-free during the intermittent timepoints.

4.4.1.7. Ventilator-free Days up to Day 28

A participant is considered ventilator-free on a day if they are not using invasive mechanical ventilation as derived from the worst case ventilation record on a day as detailed in Section 6.3.2.1.

Intermittent data is expected after discharge from investigator site, therefore if participants have discontinued ventilation and have been discharged to a non-hospitalized residence, they will be considered to be ventilation-free during the intermittent timepoints.

4.4.1.8. Admission to ICU up to Day 28

Participants will meet the endpoint if they have been admitted to the ICU at any point up to (and including) Day 28, only evaluated for participants not in ICU at time of dosing.

Participants who die prior to Day 28 without being admitted ICU will be considered to have met the endpoint (composite estimands strategy).

4.4.1.9. Change from Baseline in Inspired Oxygen (FiO₂) up to Day 28

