The secondary endpoint: "Time to final hospital discharge up to Day 28"	Updated secondary endpoints to include: 
 • Time to first discharge from investigational site up to Day 60 • Time to first discharge to non-hospitalised residence up to Day 60 	Final hospital discharge is not being collected. Participants may be discharged to an intermediary hospital residence hence we cannot assume discharge from the investigator site is equivalent to discharge from hospital. A post go live change was created to capture discharge to a non-hospitalised residence. eCRF guidelines were updated to clarify re-hospitalisation refers to the investigator site.
For exploratory endpoints on improvement in SOFA, Blood Oxygen Saturation (SpO ₂), Concentration of Inspired Oxygen (FiO ₂) and SpO ₂ /FiO ₂ ratio	Clarified exploratory endpoints to include recovery as part of composite strategy, i.e.: 
 • Recovery or Improvement of at Least 2 Points Relative to Baseline of Sequential Organ Failure Assessment (Sofa) Score up to Day 28 • Recovery or Improvement Relative to Baseline in Blood Oxygen Saturation (SpO₂), • Recovery or Improvement Relative to Baseline in Concentration of Inspired Oxygen (FiO₂) • Recovery or Improvement Relative to Baseline in SpO₂/FiO₂ ratio 	Clarified exploratory endpoints to include recovery as part of composite strategy.

Protocol	Reporting & Analysis Plan	
Statistical Analysis Plan	Statistical Analysis Plan	Rationale for Changes
For exploratory endpoints on Time to Improvement of at Least 2 Categories Relative to Baseline on an Ordinal Scale up to Day 60	For exploratory endpoints on Time to Improvement of at Least 2 Categories Relative to Baseline in Clinical Status up to Day 60	Clarified exploratory endpoints to use clinical status rather than ordinal scale for consistency

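### For participants transferred to another hospital on respiratory support, the Part 2 SAP can score days between contacts as no support, against its own rule for the day-count endpoints

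*SAP*

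**What the plan says.** Section 6.3.2.1 of the Part 2 SAP builds ventilation status for each of Days 1 to 60 from the start and end dates in a log. It has two default rules. The first is "Ventilation statuses with missing end-dates will be assumed ongoing". The second is that "participants with no open ventilation logs will be assumed to have Ventilation=None". The one route to a missing value is this: "Ventilation status will only be missing after last contact for subjects who have withdrawn from the trial". Neither default depends on where the participant is.

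The neighbouring text does depend on location. For oxygen-free days (Section 4.4.1.6), participants who have discontinued oxygen and "have been discharged to a non-hospitalized residence, they will be considered to be oxygen-free during the intermittent timepoints". Section 4.4.1.7 has the matching rule for ventilator-free days.

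Protocol Section 1.4 (Part 2 schedule, footnote 2) ends daily assessment at discharge, or at Day 28 for those still in hospital. Protocol Section 7.2.7 recognises discharge to a hospitalized facility as one of two discharge categories. The Part 1 SAP (Section 1.1, Table 2) explains why this matters: "Participants may be discharged to an intermediary hospital residence hence we cannot assume discharge from the investigator site is equivalent to discharge from hospital".

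**The concern.** A participant can leave the investigator site on oxygen, be admitted elsewhere and remain in the study. No rule addresses that participant's days between contacts. Under Section 6.3.2.1 their value depends on whether the log carries an end date. With an end date, the days count as no support; without one, they carry the last recorded level forward. While the participant has not withdrawn, they are never treated as missing.

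The no-support default also makes the restriction in Sections 4.4.1.6 and 4.4.1.7 ineffective, because it assigns the same value without asking whether the participant went home. At stake are the exploratory ventilation endpoints, the dating of two secondary time-to-event endpoints (one in the testing hierarchy) and, in a narrow case, the primary endpoint.

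**Working it through.** **1. The plan's own figure.** The documents give no transfer rate and no log-closure practice, so there is no stated figure to reproduce on this point. The Part 2 sample size is not in dispute, but it is the base for the illustration in step 4. With 45% versus 60% and one-sided 2.5%:

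n per arm = [1.960 × √(2 × 0.525 × 0.475) + 0.842 × √(0.45 × 0.55 + 0.60 × 0.40)]² / 0.15² = 172.8, rounded up to 173.

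This gives 346 in total and power of 80.05%, as stated.

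**2. The rules side by side.** Take a participant transferred on Day 10 on high-flow oxygen and still in the study.

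| Text (Part 2 SAP) | Days between contacts after transfer |
|---|---|
| 6.3.2.1, log has an end date | No support |
| 6.3.2.1, log has no end date | High-flow carried forward |
| 4.4.1.6 and 4.4.1.7 | Gap assumption does not apply: support not stopped, not discharged home |
| 4.4.1.9 (change in FiO₂) | Non-responder if discharged to advanced facilitated care |
| 6.3.2.3 (deriving FiO₂ from flow rate) | Only before discharge from the investigator site |

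Only 6.3.2.1 takes no account of location.

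**3. Endpoint by endpoint.**

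- *Oxygen-free and ventilator-free days, invasive ventilation, extubation* (exploratory): read directly from the ventilation record.
- *Time to last oxygen dependence* (4.3.1.6): where clinical status is unknown, the fallback is the last day on which oxygen was needed. A log end date entered at transfer becomes that day.
- *Time to recovery from respiratory failure* (4.3.1.4; test 4 in Section 2.1): missing clinical status before last contact is derived under 6.3.2.2. Category 3 requires a day after last oxygen use and before discharge to a non-hospitalized residence. With a log ended on Day 10 and discharge home on, say, Day 20, Days 11 to 19 become category 3 unless a score was collected. Recovery is then dated at Day 11. If the Day 14 call records category 5, recovery cannot be dated before Day 15. A participant who never goes home has no date for the category 3 rule, so no category is derived.
- *Primary endpoint* (4.2.1): the derivation acts only if no ordinal score falls in the Day 26 to 30 window (6.3.1).

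**4. Illustrations of size (assumptions, not estimates).**

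*Day counts.* With no information after transfer, days credited to Day 28 = 28 − transfer day: 21, 18 or 14 for transfer on Day 7, 10 or 14 with the log ended, and 0 with the log open. For the Day 10 case, an informative Day 14 call cuts the first gap to Days 11 to 13 (3 days). The next gap is Days 15 to 27 (13 days), before the Day 28 call.

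*Arm means.* Suppose 3% to 10% of participants are transferred on support with the log ended, and each is credited 14 days. The mean rises by 14 × 0.03 = 0.4 to 14 × 0.10 = 1.4 days. The between-arm shift is 14 × (difference in that share): 0.7 days for a 5-point difference, and none if the shares are equal.

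*Primary.* Let t be the share of each arm whose Day 28 outcome is set by log state alone, with equal log closure in both arms. The difference becomes (1 − t) × 15 points.

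| t | Difference (points) | Power with 173 per arm |
|---|---|---|
| 2% | 14.7 | about 78% |
| 5% | 14.25 | about 76% |
| 10% | 13.5 | 71-72% |

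Here t counts only transferred participants with no score in Days 26 to 30, so it is smaller than the transfer rate.

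**The case against.** The strongest reply is that these participants are not out of sight. The Part 2 schedule marks ventilation status and ordinal scale at the follow-up calls, and calls replace the Day 14 and Day 28 visits after early discharge. That stands, and it limits every gap. It does not close them: Protocol Section 7.2.4 and the schedule note word the recording of oxygen at calls for people discharged from hospital or using it at home. Recording of inpatient oxygen elsewhere between calls is therefore not assured.

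Four stronger readings are tempting, and the documents do not support them.

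- *All unobserved time is scored as best or worst, and never as unknown.* An open log carries the last level forward. That may be low-flow oxygen, which is category 4 and a primary-endpoint response. Withdrawn participants do become missing after last contact, and Protocol Section 6.8 includes those lost to follow-up: "Should the participant continue to be unreachable, he/she will be considered to have withdrawn from the study".
- *Patients who are transferred and then die are credited with recovery.* Section 6.3.2.2 sets category 8 from the date of death, and Sections 4.3.1.4 and 4.3.1.6 censor deaths at Day 28. For them only the exploratory day counts can move.
- *Sites do close logs at transfer.* No text says so. The study reference manual, eCRF guidelines and programming specification may cover it, and they are not available here.
- *The treatment comparison is biased by as much as the credited days.* That would need nearly all such transfers, or log closures, to fall in one arm of a randomized, double-blind trial.

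It can also be argued that 4.4.1.6 and 4.4.1.7 govern their own endpoints whatever 6.3.2.1 says. That reading is possible, but both sections take their values from the record that 6.3.2.1 defines, so the plan should say which rule prevails.

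**Conclusion.** The point holds in a limited form. For a participant discharged to a hospitalized facility on support and still in the study, Section 6.3.2.1 fills days between contacts with no support or the last recorded level, according to log state. The no-support default conflicts with Sections 4.4.1.6 and 4.4.1.7. The effect is direct on exploratory endpoints. It can reach the dates of last oxygen dependence and, for those who later go home, of recovery from respiratory failure. It reaches the primary only through a missed Day 26 to 30 score.

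The size cannot be established. The figures above rest on assumed transfer shares, assumed log closure and, for the 14- to 21-day counts, calls that yield no information. The case for acting is that an inconsistent rule touches a hierarchy-tested endpoint and is cheap to correct.

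**What to change.** In Part 2 SAP Section 6.3.2.1, restrict the no-support default to three kinds of day:

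- days at the investigator site;
- days after discharge to a non-hospitalized residence with support stopped;
- days for which a later contact confirms that no support was used.

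State that a log end date equal to the date of transfer to a hospitalized facility does not by itself count as stopping support.

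For participants transferred on support, leave unconfirmed ventilation status and derived clinical status (6.3.2.2) missing until the next contact. Then:

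- scheduled-visit endpoints go to the existing multiple imputation;
- time-to-event dates use the confirmed stop date or, failing that, the date of the confirming contact;
- unconfirmed days do not count as oxygen-free or ventilator-free, in line with 4.4.1.6 and 4.4.1.7. This has to be written down, because the imputation in 6.2.1 works on scheduled visits and does not cover daily counts.

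The cost is SAP wording, a few more imputed visit values, and slightly later recovery dates for some transferred participants.
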